Intervention. The intervention will be the enhanced Transport Canada booster seat material that was developed in the previous phase. The intervention material will be the same as the one for the control group in all respects (font size, formatting, etc.), except that it will contain an introduction explaining, in plain language: (a) seatbelts redirect crash forces to the child's thorax and pelvis; (b) booster seats ensure children wear the seatbelt correctly across the hips and chest; and (c) booster seats, used in combination with the seatbelts, prevent injuries to head, neck, spine, abdomen, internal organs, as well as injuries resulting from ejection. The final version of these introduction and accompanying figures will be decided, based on input from the focus groups.

Outcome measures. The primary outcome measures are perceived safety benefit of booster seats and intention to use them, as assessed by the Booster Seat Attitudes Scale (BSAS).²⁰ The BSAS has been validated and tested in a Canadian sample of parents, and the Benefit and Intent subscales of the BSAS reported good internal consistency (Cronbach's alpha of 0.85 and 0.84, respectively). Secondary outcome measures are information recall (when it is safe to start using a booster seat, how to install it, how to use it, and when it is safe for a child to use only the seatbelt) and self-efficacy (as measured by the Perceived behavioural control subscale of the BSAS; Cronbach's alpha of 0.87), their subjective estimates of the risk reduction afforded by booster seats (from 0 to 100%), their subjective estimate of the impact of the intervention on other parents, time they spend reading the material, clicks on links to additional booster seat information.

UPDATE 27 OF JUNE 2019: Factor validation of the BSAS revealed that using the Benefit subscale actually comprises Perceived Benefit (i.e., understanding that booster seats prevent injuries) and Key Benefit (i.e., understanding that booster seats prevent life threatening injuries to the spine and abdomen). Similarly, the Intent subscale of the BSAS was found to have factors: Intent to Use and Intent to Learn (i.e., intention to attend a car seat clinic or workshop). The projected intent scale, developed for this study also had two factors: Projected intent to use and projected intent to learn. These new subscales constitute the updated outcome measures.

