Participants. 303 mothers and 303 fathers of children 4 to 8 years old residing in any Canadian province, who speak English and drive with their child at least once a month. Participants will be excluded if their child has a physical condition that requires special transportation. Parents will be invited to participate, irrespective of whether they use booster seats always, occasionally, or never. A sample of 606 participants provides sufficient power to detect a mean difference of 0.4 points in the Benefit subscale of the BSAS. This difference in benefit scores has been found to distinguish those parents who consistently restrain their child in booster seats from those who do not. Sample size was estimated with the TwoSampleMean function for trials that test superiority of interventions (TrialSize package for R). Participants in the trial will receive \$1/each for the completion of the survey. Based on information from studies with similar characteristics, the expected response rate is 40%.

Setting and Procedures. The trial will be conducted entirely online. The online trial will be pilottested with a sample of 10 parents, recruited through the same procedure used for the focus groups. Each participant will be asked to complete the online trial, in the presence of a researcher, at their home, office, or the researcher's lab located in the BC Children's Hospital. Each participant will be asked to speak out loud as he or she navigates the online trial. The researcher will ask probing questions if participants understand the question in an unintended way, do not understand what they are supposed to do, move the mouse erratically, or express frustration and/or confusion. Participants will then be debriefed to identify any potential misunderstanding of the information provided (e.g., incorrectly inferring that seatbelts are inherently dangerous for children rather than necessary safety devices that must be used in combination with booster seats). At the end of the pilot test, participants will receive \$40/each. The online questionnaire and education material will be improved or corrected, as appropriate.

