- 6. Participants in the control group will be given the option to view the enhanced booster seat material, in order to give them the opportunity to benefit from the intervention.

Analysis. The online version of the Booster Seat Attitudes Scale will be factor-validated and Cronbach's alpha of each BSAS subscale will be calculated to determine reliability. The effect of the intervention on the Benefit, Intention, and Self-Efficacy subscales of the BSAS will be examined through linear mixed effects models with random effects by province (to account for between-province differences in legislation and booster seat education programs). Multiple imputation will be used to address missing data. Intention-to-treat analysis will be conducted, by doing two separate analyses: one with the entire sample of participants and one with only participants who complete the trial. In addition, mediation analysis will be conducted to determine if perceived safety benefit mediated the effect of the intervention on intent to use booster seats. Dropout curves will be used to examine in which part of the trial participants in each condition were more or less likely to drop out. *Student's t, Wilcoxon Sign and Rank*, or *Mann-Whitman's U* tests will be used to compare, across groups, subjective estimates of the impact of the intervention on other parents, time spent reading the material, number of clicks on links to additional booster seat information, and pre- versus post-intervention difference in subjective estimates of the risk reduction afforded by booster seats and by seatbelts.

UPDATE 27 OF JUNE 2019:

Increase in perceived safety benefit of booster seats (primary outcome) and increase in intention to use booster seat (a secondary outcome) were evaluated by, first calculating the difference between the post-intervention score and the pre-intervention score for each participant. This difference was then compared with t tests (two-tailed). Parents' judgments of the impact of the intervention on their peers (a secondary outcome), which was assessed post-intervention only, was compared across study arms with the t tests (two-tailed). The same statistical analysis was used to evaluate the other secondary outcomes (parents' recall of booster seat information, Interest in booster seat information).

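### The June 2019 update reports a primary analysis written down after it was run in place of the planned one, and leaves the primary Benefit subscale and the main missing-data method unclear

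*Combined protocol and SAP*

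**What the plan says.** **Planned text.** The Outcome measures section states: "The primary outcome measures are perceived safety benefit of booster seats and intention to use them", both measured by BSAS subscales. The Analysis section says that the effects on Benefit, Intention and Self-Efficacy "will be examined through linear mixed effects models with random effects by province", justified by differences in provincial legislation and education programs. It adds: "Multiple imputation will be used to address missing data". Factor validation of the online BSAS is also planned, with no rule for what follows if the factors differ from the published subscales.

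**Update of 27 June 2019.** Under Outcome measures: "Factor validation of the BSAS revealed that using the Benefit subscale actually comprises Perceived Benefit" and a second factor, Key Benefit. Intent is likewise split, into Intent to Use and Intent to Learn, and the new subscales are declared to be the outcome measures from then on. Under Analysis, perceived benefit is the primary outcome, while "increase in intention to use booster seat (a secondary outcome" in the update's own parenthesis. Both "were evaluated by, first calculating the difference between the post-intervention score and the pre-intervention score for each participant", followed by two-tailed t tests. Intention-to-treat is reported as two further analyses in which dropouts receive the highest or the lowest possible score.

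Both updates stand inside the operative sections, and the planned text remains beside them.

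**The concern.** The update's past tense describes completed work, so the test it presents as primary was put in writing after the analyses had been run. If that test stands alone as the headline, a reader has no protection against a choice among outcomes, hierarchies and models, and cannot see whether the planned analysis gives the same answer. Nothing in the document says that the planned analysis was carried out.

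Two gaps make this worse. The update calls perceived safety benefit primary just after dividing it into two factors, without saying whether Perceived Benefit, Key Benefit or both carry the test. And because multiple imputation is not mentioned while the extreme-score runs are described as additional, the main handling of dropouts is unknown.

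**Working it through.** **1. Plan and update side by side**

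| Element | Planned | Update | Reason given |
|---|---|---|---|
| Primary outcomes | Benefit and Intent | Perceived benefit only; intention secondary | None |
| Scales | Original Benefit and Intent subscales | Two factors from each | Factor validation |
| Test | Linear mixed model, random effects by province | Two-tailed t test on change score, no province term | None |
| Missing data | Multiple imputation; whole-sample and completer analyses | Highest-score and lowest-score runs, as additional analyses | None |
| Other outcomes | Include self-efficacy and 0-100% risk estimates | Neither is named | None |

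Every row differs. Only the second gives a source, and that source is data.

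**2. The plan's own figure**

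The Participants section plans "303 mothers and 303 fathers of children 4 to 8 years old residing in any Canadian province" and says: "A sample of 606 participants provides sufficient power to detect a mean difference of 0.4 points in the Benefit subscale of the BSAS". SD, alpha and numerical power are not stated, so 606 can be neither reproduced nor refuted. With 1:1 allocation (implied under Ethical considerations), n = 606/2 = 303 per arm. At an assumed two-sided 0.05, the SD that would make the statement true is

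SD = 0.4 / [(1.960 + z_power) × √(2/303)]

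- 80% power: 0.4 / [(1.960 + 0.842) × 0.0812] = 1.76
- 90% power: 0.4 / [(1.960 + 1.282) × 0.0812] = 1.52

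Whatever the true inputs, the 0.4 points and their stated link to consistent booster use belong to the original Benefit subscale. They are not restated for either new factor or for a change score.

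**3. Error rate of the primary claim**

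*Two original primaries, each at 5%, unadjusted.* Independent: 1 − 0.95² = 9.75%. With correlated normal test statistics, 1 − P(|Z₁| ≤ 1.96, |Z₂| ≤ 1.96) gives 9.5% at correlation 0.3 and 8.3% at 0.7 (assumed).

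*Updated primary.* Null simulation with 303 per arm, 8,000 runs per setting and no dropout. The original Benefit scale is the mean of the two factors, and a baseline-adjusted regression without a province term stands in for the mixed model. Both correlations are assumptions.

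| Factor corr. | Pre-post corr. | Planned-type test alone | t test, one new factor | Either new factor | Planned or either new factor |
|---|---|---|---|---|---|
| 0.3 | 0.5 | 4.8% | 4.9% | 9.6% | 11.6% |
| 0.3 | 0.7 | 4.8% | 4.9% | 9.2% | 10.9% |
| 0.5 | 0.5 | 5.5% | 5.2% | 9.1% | 11.3% |
| 0.5 | 0.7 | 4.9% | 4.5% | 8.6% | 10.1% |
| 0.7 | 0.5 | 5.3% | 4.8% | 8.0% | 9.9% |
| 0.7 | 0.7 | 5.3% | 5.0% | 8.4% | 9.7% |

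The Monte Carlo standard error is √(0.05 × 0.95/8000) = 0.24 percentage points near 5% and √(0.10 × 0.90/8000) = 0.34 near 10%. A single test fixed in advance therefore holds its level, whichever test it is. The excess comes only from leaving the choice open.

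**The case against.** The best defence is that the changes are dated and visible, and the planned text was left in place. Factor validation was planned. The Blinding section says that researchers stay blinded through the analysis; choices made in that state would carry little bias. The t test is on change from baseline, so baseline enters it, and such a test is valid when fixed in advance. The trial was also sized as a two-sample comparison of mean Benefit, so a two-arm comparison led by Benefit is not foreign to the design.

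Much of this stands, and it rules out several stronger readings that a reader might infer:

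- *That results drove every change.* This is documented for no change. The subscale split came from data, through a planned step. For the test, the hierarchy and the missing-data method, the documents show late documentation and no more.
- *That multiple imputation was replaced by extreme values.* The extreme-score runs are described as additional sensitivity analyses, and multiple imputation is dropped only by implication.
- *That the intervention shaped its own endpoint through the factor analysis.* Key Benefit does match the taught content, but the same injuries belong to the prior hypothesis, and nothing says that post-intervention responses were used. A pre-randomization BSAS exists (step 1 of the procedures).
- *That the false-positive risk is 26%.* Six subscales are named, and 1 − 0.95⁶ = 26.5%, but that family pools the primary outcome with secondary ones.

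What the defence does not supply is a date for unblinding relative to these choices, a reason for the change of model or hierarchy, or a statement that the planned analysis was run.

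**Conclusion.** The point holds as one of pre-specification and reporting. The operative headline test was written down after the analyses. It differs from the plan in scale, hierarchy and model, and it leaves two things undefined: which Benefit factor is primary, and how missing data are handled in the main analysis.

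The size is moderate. If either Benefit factor could count, the risk is no worse than under the original two unadjusted primaries; adding the planned test to the choice raises it slightly. These figures rest on assumed correlations, complete data and a simplified stand-in for the mixed model. They describe exposure if the choice was open. Whether it was open depends on when unblinding occurred, so a loss of the 5% level is possible but not established.

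**What to change.** - Report the planned analysis first or beside the updated one: mixed model with province effect and multiple imputation, on the original Benefit and Intent subscales as the two primary outcomes.
- Label the June 2019 subscales, hierarchy and t tests as post hoc.
- Name one Benefit subscale as primary, or apply a multiplicity adjustment such as Holm. No such rule exists in the plan, so identify it as a new addition.
- Derive the factor solution from the step 1 BSAS, before randomization and pooled over arms, and say so.
- State when the factor analysis and the unblinding took place, and which missing-data method the main analysis uses.
- Report every outcome listed before the update, including self-efficacy and the 0-100% risk estimates.

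The cost is re-analysis of data already held, plus text. The downside is that the headline may become less favourable and the new subscales exploratory. If the two analyses agree, the conclusion is stronger for it.

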Procedure. The new booster seat information material will be created by taking Transport Canada's⁴⁴ online material (click here to open link) and then by adding an introduction that explains: (a) seatbelts redirect crash forces to the child's thorax and pelvis; (b) booster seats ensure children wear the seatbelt correctly across the hips and chest; and (c) booster seats, used in combination with the seatbelts, prevent injuries to head, neck, spine, abdomen, internal organs, as well as injuries resulting from ejection. See Appendix 1. Three focus group interviews (one with fathers only, one with mothers, and one mixed) will be conducted to test the enhanced material. Focus group discussions will revolve around knowledge and beliefs about booster seats and seatbelts, as well as opinions regarding the content, wording, and format of the education material.

Analysis. The focus group interviews will be audio recorded and participants' feedback will be used to improve the material's *concept* (i.e., whether the message produced the intended effect) and *execution* (i.e., whether the material effectively conveys the intended message), as appropriate.

Randomized Controlled Trial

Objective. To determine if the enhanced Transport Canada online material is better than the current version at increasing perceived safety benefit and intention to use booster seats.

Design. An internet-based Phase II proof-of-concept trial (with a control group) will be conducted, in order to test if the intervention produces the intended psychological effect. The trial will use a concurrent two-group parallel randomized controlled design. The use of a control group is necessary to address threats to validity stemming from repeating observations on the same participants: learning and carry-over (i.e., learning something in the first question that then informs subsequent answers), sensitization (i.e., becoming more sensitive to differences by subsequent questions), and demand effects (i.e., noticing that the researcher wants a different response in the second question).

Randomization. Randomization schedule will be generated using the sealedenvelop.com. Randomization will be stratified by province, gender, and socioeconomic status. Additionally, randomization will be blocked to ensure balanced groups throughout allocation.

Blinding. Both researchers and participants will be blinded to allocation, even during data analysis.

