After pilot-testing is complete, participants will be recruited through an online market research firm, Maru/Matchbox, which maintains a nationwide panel of 130,000 individuals whose distribution represents the Canadian population. Maru/Matchbox will send an email invitation to participate along with a link to the online survey. The landing page of the survey will provide description of the study for parents to read. The online survey will be set up in such a way that participants won't be able to start answering questions, unless they consent by clicking the "I

agree" button. Participants, will be advised to print and keep a copy of the consent form either as PDF or as hard copy. After consenting to participate, the online trial will proceed as follows:

- 1. Participants will complete a demographics questionnaire, the BSAS, and four questions on booster seat guidelines (e.g., minimum and maximum ages, heights, and weights to determine when a child should use a booster seat, and when it is safe for a child to use only the seatbelt).
- 2. The system will randomly assign the participant to either the intervention or the control group. Randomization will be stratified by sex, child age, and jurisdiction to ensure both groups are equal. This stratification is necessary because, in Canada: (a) fathers and mothers differ in their attitudes regarding child vehicle safety,⁴⁵ (b) booster seat use decreases as the child gets older,⁴⁶ and (c) provinces differ from one another in terms of legislation and booster seat education programs.⁴⁷
- 3. Participants in the intervention group will be presented the enhanced booster seat material, while participants in the control group will be presented the current Transport Canada booster seat material. Material provided to both groups will be stripped of logos (Transport Canada logos and corporate identity), but will be properly cited.
- 4. Participants will complete again the BSAS and the questions on booster seat guidelines.
- 5. Participants in the intervention group will be asked one or two multiple choice questions to ensure they did not misunderstood the information in an unintended way. These questions will be designed based on the information on adverse effects collected during the focus groups and the trial's pilot. If a parent answers incorrectly, the system will clarify the information immediately after.

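### The June 2019 change-score t tests are valid, but they fix the baseline slope at 1 and omit the randomisation factors; a baseline-adjusted regression would be modestly more precise at no data cost.

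*Combined protocol and SAP*

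**What the plan says.** The update of 27 June 2019 in the Analysis section describes the test of perceived benefit (primary) and intention to use (secondary) in two steps: "first calculating the difference between the post-intervention score and the pre-intervention score for each participant", and then "This difference was then compared with t tests (two-tailed". It names no baseline covariate, province term or stratification factor.

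The text before the update in the same section planned "linear mixed effects models with random effects by province (to account for between-province differences in legislation and booster seat education programs". That model states no baseline term, and the update does not say whether it still applies.

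Baseline data exist by design. Under Setting and Procedures, step 1, before allocation, "Participants will complete a demographics questionnaire, the BSAS, and four questions on booster seat guidelines". Step 4 repeats the BSAS and the guideline questions after the material has been shown.

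Allocation is stratified and blocked, but the factors differ between sections. Randomization says: "Randomization will be stratified by province, gender, and socioeconomic status". Setting and Procedures, step 2, says: "Randomization will be stratified by sex, child age, and jurisdiction to ensure both groups are equal".

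For recall, the update says "The same statistical analysis was used to evaluate the other secondary outcomes". That sentence directly follows the test of the peer-impact judgement, which is measured only after the intervention.

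The sample size statement under Participants reads "A sample of 606 participants provides sufficient power to detect a mean difference of 0.4 points in the Benefit subscale of the BSAS". It gives no SD, significance level, numerical power or pre-post correlation.

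**The concern.** A change score is a regression on baseline with the slope set to 1 instead of estimated. Unless the true slope is 1, the subtraction puts baseline noise into the outcome that a fitted slope would remove. The data needed to fit it are already in hand.

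The t test also ignores the factors used in allocation, although step 2 of Setting and Procedures justifies stratifying by parent's sex, child age and province on the ground that these matter. Stratified allocation reduces the true variance of the treatment difference when the factors predict the outcome. A test that omits them does not credit this, so its standard error tends to be too large. Differencing removes stable level effects, so this part may be small.

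At stake is the width of the intervals for the primary outcome and intention to use, and an analysis that does not reflect the randomisation. Bias and false positives are not at issue. For recall, if the test is post-only, the pre-intervention guideline answers go unused.

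**Working it through.** **The plan's own figure.** The 606 can be neither reproduced nor refuted, because SD, significance level, power and margin are not given. It can be inverted. Take 303 per arm (the ethics section says half the participants will not be exposed to the intervention), a 0.4-point difference in levels, and assume two-sided 5% and 80% power:

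SD = 0.4 / ((1.960 + 0.842) × √(2/303)) = 1.757.

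Other assumptions give 1.52 (two-sided 5%, 90% power) or 1.98 (one-sided 5%, 80% power).

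**Precision from baseline.** With s the common pre and post SD:

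- change score: per-person variance 2s²(1 − rho)
- post score adjusted for baseline: s²(1 − rho²)
- variance ratio, adjusted to change: (1 + rho)/2; interval-width ratio: its square root
- sample size at which the adjusted analysis matches the t test on 606: 606 × (1 + rho)/2

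Rho is assumed. Because both scores come from one online session, 0.7 to 0.9 is taken as plausible, and 0.5 is shown as a lower case. Half-widths are 1.96 × SD of the outcome × √(2/303) with s = 1.757. Power is for 0.4 points at two-sided 5%.

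| rho | variance ratio | width ratio | equivalent n | 95% half-width, change → adjusted | power, change → adjusted |
|---|---|---|---|---|---|
| 0.5 | 0.75 | 0.866 | 454.5 | 0.28 → 0.24 | 80.0% → 89.9% |
| 0.7 | 0.85 | 0.922 | 515.1 | 0.22 → 0.20 | 95.1% → 97.5% |
| 0.8 | 0.90 | 0.949 | 545.4 | 0.18 → 0.17 | 99.3% → 99.7% |
| 0.9 | 0.95 | 0.975 | 575.7 | 0.125 → 0.122 | above 99.9% for both |

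If instead the change-score test itself is assumed to have 80% power, the adjusted analysis has 90%, 86%, 84% and 82% at these four values of rho.

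**Unequal SDs.** In general the variance saved is s_pre²(1 − beta)², where beta = rho × s_post/s_pre. In large samples this is never negative. If the post SD is 0.8 of the pre SD, as a ceiling effect might produce, the variance ratio falls to 0.571, 0.628 and 0.640 at rho 0.5, 0.7 and 0.8. If the post SD is 1.25 times the pre SD and rho is 0.8, beta = 1 and the gain is zero.

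**Stratification factors.** These figures are simulated with assumed effects: 2,000 trials per scenario, 606 parents, permuted blocks of 4 within sex × two child-age bands × ten provinces. The table gives the reported variance relative to the t test, with baseline only and then baseline plus factors.

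| rho | factors affect levels only | factors explain 5% of change variance |
|---|---|---|
| 0.7 | 0.866, 0.855 | 0.873, 0.812 |
| 0.8 | 0.911, 0.905 | 0.916, 0.859 |
| 0.9 | 0.956, 0.955 | 0.959, 0.907 |

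The factors therefore add 0 to 1 percentage point in the first case and 5 to 6 in the second.

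**Validity.** Type I error of the t test in that simulation was 4.3% to 5.9%, with simulation error of about 1 point (1.96 × √(0.05 × 0.95/2,000) = 0.0096). A second simulation, with 20 strata and 4,000 runs per scenario, gave 4.4% to 5.2% without stratum effects and 3.5% to 4.5% with them. The adjusted regression gave 4.6% to 5.0%. There is no sign of inflation, and the t test is somewhat conservative when strata matter. The second simulation also reproduced the formula: variance ratios of about 0.74, 0.84 to 0.86, and 0.95 at rho 0.5, 0.7 and 0.9.

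**The case against.** The strongest reply is that there is no error to correct. A two-sample t test on change is an accepted analysis of an increase in score. In the range called plausible the half-width shrinks by only about 0.02 to 0.003 points against a 0.4-point target, and power is already at least 95%. This stands, and it is why the point is about efficiency only.

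The point-scale figures are also open to challenge. The 0.4 points and the implied SD belong to the undivided Benefit subscale, whereas the June 2019 update under Outcome measures splits it into Perceived Benefit and Key Benefit. The half-widths and power figures are therefore conditional illustrations and do not describe the updated primary outcome. The variance ratio does not depend on the scale, but it does depend on rho and on the ratio of post to pre SD. The word *modestly* therefore rests on those assumptions: the gain could be zero or well above the central figures.

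The stratum effects are assumed and use only the step 2 factors, so socioeconomic status was not simulated.

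Finally, the update is in the past tense. If results are known, an adjusted analysis added now carries less weight. The conflicting factor lists, the unclear recall test and the status of the mixed model are documentation gaps in their own right. They matter here because the adjusted model cannot be specified until they are settled.

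**Conclusion.** The concern holds as a matter of precision. The change-score t tests are unbiased and keep their type I error, but they use baseline less efficiently than the collected data allow and do not reflect the stratified randomisation. With equal SDs and rho of 0.7 to 0.9, baseline adjustment cuts the variance by 15% to 5% and narrows intervals by 8% to 2.5%. At rho 0.5 the figures are 25% and 13%, and only there is the power gain material under the implied SD of 1.76. The stratification factors add little if they affect levels only, and 5 to 6 points of variance if they explain 5% of the change variance.

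Rho, the SDs and the stratum effects are all assumptions, so confidence in the size is medium. The direction does not depend on them: in large samples, estimating the slope cannot lose precision. The change should be made because it is nearly free, not because the current test misleads.

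**What to change.** 1. Reconcile the stratification lists in Randomization (province, gender, socioeconomic status) and in Setting and Procedures, step 2 (sex, child age, jurisdiction), and record which factors were actually used.
2. For each outcome measured before and after (BSAS subscales and guideline recall), report a linear regression of the post score on arm, the same baseline score and those factors, two-sided 5%, beside the change-score t test. The same model suits the risk-reduction estimates if they are still analysed as a pre-to-post difference. The peer-impact judgement has no pre score, so only the factors could be added there.
3. Make the regression primary only if results have not been seen. Otherwise keep the t test as the stated primary and label the regression as an adjusted analysis added after the update.
4. State whether the recall test uses change or post-only scores, and whether the mixed model with a province effect still applies.

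The cost is SAP wording and a small re-analysis, with no new data. It uses one degree of freedom for baseline and up to about 11 for the factors (sex 1, linear child age 1, ten provinces as fixed effects 9), so about 12 with 606 parents. The estimate remains a mean difference in points.
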